9.6.1 Safety Variables of Analysis

9.6.1.1 Adverse Events

Definitions:

- A *treatment-emergent adverse event* (TEAE) is an event that is observed or reported after administration of study medication that was not present prior to study medication administration or an event that represents the exacerbation of a pre-existing event.
- An *adverse withdrawal* is a subject who withdrew from the study due to an adverse event.
- A *serious adverse event* (SAE) is an AE that is classified as serious according to the criteria specified in the study protocol.

Adverse events variables of analysis include:

- Proportions of subjects with TEAEs by Preferred Term and decreasing frequency of TEAE
- Proportions of subjects with TEAEs by System Organ Class and Preferred Term
- Proportions of subjects with adverse withdrawals

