### 4.2.1 Treatment-emergent Adverse Events

Adverse events will be coded using Medical Dictionary for Regulatory Activities (MedDRA) Version 16.0 or above. Adverse event coding will be done to the lowest level term (LLT). Adverse events will be summarized by System Organ Class (SOC) and preferred terms (PT).

Definitions:

- A treatment-emergent adverse event (TEAE) is an event that is observed or reported after administration of study medication that was not present prior to study medication administration or an event that represents the exacerbation of a pre-existing event.
- An adverse withdrawal is a subject who withdrew from the study due to an adverse event.
- A serious adverse event (SAE) is an AE that is classified as serious according to the criteria specified in the study protocol.

Safety and tolerability variables based on adverse events include the following:

- Proportions of subjects with TEAEs by Preferred Term and decreasing frequency of AEs
- Proportions of subjects with TEAEs by System Organ Class and Preferred Term
- Proportions of subjects with related TEAEs
- Proportions of subjects with severe TEAEs
- Proportions of subjects who died.
- Proportions of subjects with treatment-emergent SAEs other than death.
- Subjects with TEAEs that result in study termination.

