Rank analogues (e.g., Wilcoxon analysis, rank ANCOVA, and van Elteren analysis when strata are a part of the approach) will be used for additional supportive analyses. An observed-cases analysis will be done by visit.

An essential component of the thorough analysis includes an assessment of the impact of missing data on study conclusions. As a part of assessing this impact, sensitivity analysis will include an endpoint analysis (reduction to last-observation-carried-forward, justified in this study based on the monotonic progression of the natural course of AD and assuming no more dropouts in the group treated with azeliragon plus SoC than in the group treated with placebo plus SoC), a completers analysis (observed cases at Month 18), and observed cases by assessment time.

Interaction terms will be examined in the supportive analyses. The primary model will not include interaction terms with covariates. In the event of a significant interaction term, the impact on analysis conclusion will be examined. A key sensitivity analysis will use the ITT methodology and a main-effects model for ANCOVA adjusting for baseline ADAS-cog (CDR-sb) using last-observation-carried-forward (LOCF) methods for missing data, justified based on known profiles of ADAS-cog (CDR-sb) in AD patients, which is conservative under the assumption that there are not more dropouts in the active-treated group than the placebo group. Rank ANCOVA will be done as a supportive analysis.

Additional unplanned sensitivity analyses may be performed.

Descriptive summaries will be produced of the observed values and change from Baseline in co-primary variables by treatment group at each individual time point and at endpoint (final on-treatment assessment for each subject).

For statistical analyses, 95% confidence intervals will be produced for the least-squares means (LSM) in each treatment group, as well as the LSM differences as compared to placebo plus SoC. For MMRM and ANCOVA, two-sided p-values will be displayed for the comparison against placebo plus SoC.

Because there are limited numbers of subjects per center, there will be inadequate power to explore the impact of the center effect on study conclusion. Descriptive statistics by center will be presented.

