### **5.4 Analysis of Safety Data**

#### **5.4.1 Adverse Events**

Adverse events reported in this study will be coded using MedDRA®, Version 16.0, or later. Coding will be to the lowest level terms (LLT). The verbatim text, the preferred term, and the primary system organ class (SOC) will be listed in subject listings. Summaries that include frequencies and proportions of patients reporting AEs will include the preferred terms and the SOCs. Summaries will include TEAEs by severity and by relationship to study medication.

Adverse event summaries will be constructed displaying AEs in decreasing order of total frequency according to the numbers of subjects reporting the AE (not the number of reports).

- Number (percent) of subjects reporting TEAE by treatment and overall in accordance with variables listed in [Section 4.1.1](#).

Supportive listings will be constructed that includes the subject identification, the treatment group, TEAEs, MedDRA terms, seriousness, severity, causality, elapsed time to onset, duration, and outcome.

Methodology for AESIs will follow the same methodology for TEAEs.

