### **6.5 Early Termination Assessments and Follow-up Assessments**

When a patient withdraws from the study prematurely for any reason, an early termination (ET) visit is to be performed, except in the case when a patient withdraws consent (and the protocol specifically states that no further data would be collected). An ET visit should be “on treatment,” and efficacy data collected at the ET visit are suitable for use in statistical analysis. Efficacy data from an ET visit will be mapped to a scheduled visit based on the study day of the ET visit using the convention that the ET is mapped to the nearest scheduled visit by date. If a subject has more than one efficacy value for a visit, the assessment closest to the target day for the visit will be used for analysis.

A follow-up visit is planned for subjects 3 months following the last dose of study medication, noting that subjects who roll-over into the open-label extension study will not have the follow-up visit, because the last day of dosing for TTP488-301 is one day before the planned first dose of medication under TTP488-303 (the protocol for the open-label extension study). Data collected at the follow-up visit are not considered “on treatment,” and the data are not suitable for use in statistical analysis (as the data can be tainted by other treatments).

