## 9 Data Displays

The plans for displaying data will conform to this guideline and also to ICH E3 (*Structure and Content of clinical Study Reports*), and to ICH E9 (*Statistical Principles for Clinical Trials*).

The following excerpt from ICH E3 (1996) applies to this SAP:

“The guidance provided below is detailed and is intended to notify the applicant of virtually all of the information that should routinely be provided so that post-submission requests for further data clarification and analyses can be reduced as much as possible. Nonetheless, specific requirements for data presentation and/or analysis may depend on specific situations, may evolve over time, may vary from drug class to drug class, may differ among regions and cannot be described in general terms; it is therefore important to refer to specific clinical guidelines and to discuss data presentation and analyses with the reviewing authority, whenever possible. Detailed written guidance on statistical approaches is available from some authorities.

“Each report should consider all of the topics described (unless clearly not relevant) although the specific sequence and grouping of topics may be changed if alternatives are more logical for a particular study” (p. 2).

In accordance with FDA and ICH guidance, tables, figures, and key data listings are planned. Exploratory and data-driven data displays may also be generated.

Planned displays will include, but are not limited to, the following:

- Summary of Accountability (number screened, enrolled, completing, withdrawn, by reason; listing of withdrawals with study day and reason)
- Summary of Demography and Background Data
- Summary of Adverse Events
- Summary of Adverse Events by severity and by relatedness
- Summary of Vital Signs (change over time; criteria of potential clinical concern)
- Summary of Laboratory Data, including LFTs (change over time, TEAV, and criteria of potential clinical concern)
- Summary of PK Data
- Summary of Plasma Amyloid-beta Data
- Summary of Efficacy Data (ADAS-cog, CDR-sb, CDR-global, MMSE, ADCS-ADL, NPI)
- Summary of MRI Data
- Summary of PET Data
- Listing of Demography
- Listing of Dosing
- Listing of all Adverse Events
- Listing of all Adverse Events that resulted in Death
- Listing of all Serious Adverse Events
- Listing of all Adverse Events resulting in Study Termination

- Listing of Treatment-emergent Abnormal Values of Potential Clinical Concern for Clinical Laboratory Data

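### Adverse events are summarised only as crude percentages of treated subjects, with no summary of exposure or time at risk; if dropout differs by arm, the arm that loses more patients will look somewhat safer than it is

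*SAP*

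**What the plan says.** SAP 5.4.1 sets the summary as "Number (percent) of subjects reporting TEAE by treatment and overall", counting subjects rather than reports. The variables behind it in SAP 4.2.1 are proportions of subjects, such as "Proportions of subjects with TEAEs by System Organ Class and Preferred Term", and Protocol 9.6.1.1 is built the same way ("Proportions of subjects with TEAEs by Preferred Term and decreasing frequency of TEAE"). For events of special interest, SAP 5.4.1 adds "Methodology for AESIs will follow the same methodology for TEAEs". The safety set in SAP 3 is everyone who took any study drug, however long they stayed.

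Timing appears only at subject level. SAP 9 names a "Listing of Dosing" and a listing of withdrawals by study day and reason. SAP 5.4.1 puts time to onset and duration in supportive listings.

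Time under observation depends on how a patient leaves. Early leavers are asked back 3 months after the last dose (Protocol 6.2.10 and 6.3). Completers who decline the extension are seen at Month 21. For the rest, SAP 6.5 has "noting that subjects who roll-over into the open-label extension study will not have the follow-up visit". The definition of a treatment-emergent event in SAP 4.2.1 starts at first dose and has no end, although SAP 6.2 defines a 45-day on-treatment window for assessments.

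**The concern.** A crude percentage over a fixed period reads as a risk only if patients are observed for similar lengths of time. Treatment lasts 18 months and the sample size allows for up to 20% dropout, so some patients will have much shorter follow-up than others. If the arms lose patients at different rates, the arm with less observation records fewer first events for that reason alone. Safety and tolerability is a stated secondary objective, and the tables as planned would not let a reader separate a lower event rate from less time at risk. The plan does consider unequal dropout for efficacy, with several missing-data analyses in SAP 5.2.1. It plans nothing comparable for adverse events.

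**Working it through.** **The plan's own figure.** The documents give no adverse-event rate, exposure or person-time. The only related figure is the pooled 20% dropout in Protocol 9.1, and the arithmetic that uses it reproduces: 304/(1 − 0.20) = 380, and 141/(1 − 0.20) = 176.25, rounded up to 177 per arm, or 354.

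**Inputs.** From the documents: T = 18 months of treatment, 3 months of follow-up for early leavers, about 400 patients per arm with both sub-studies combined. Assumed: a 10% risk over a full 18 months, the same constant hazard in both arms, exits unrelated to the event, and dropout d of 15% in one arm and 25% in the other (mean 20%). Exits are either uniform over 18 months or all at Month 4.

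**Formulas.** λ = −ln(0.90)/18 = 0.00585 per month, or 7.02 per 100 patient-years. Crude percentage = (1 − d)·p + d·q, where p = 10% is the completers' risk and q the leavers' average risk. If risk ends at exit:
- uniform exits: q = 1 − (1 − e^(−18λ))/(18λ) = 1 − 0.1000/0.1054 = 5.09%
- Month 4 exits: q = 1 − e^(−4λ) = 2.31%

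With 3 further months of observation for leavers, and completers stopping at Month 18:
- uniform exits: q = 1 − e^(−3λ)·(0.1000/0.1054) = 6.74%
- Month 4 exits: q = 1 − e^(−7λ) = 4.01%

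| Exits | Observed after exit | d = 15% | d = 25% | Ratio | Gap per 400 |
|---|---|---|---|---|---|
| Uniform | none | 9.26% | 8.77% | 0.95 | 2.0 |
| Month 4 | none | 8.85% | 8.08% | 0.91 | 3.1 |
| Uniform | 3 months | 9.51% | 9.18% | 0.97 | 1.3 |
| Month 4 | 3 months | 9.10% | 8.50% | 0.93 | 2.4 |

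First row: 0.85 × 10% + 0.15 × 5.09% = 9.26%, and 0.75 × 10% + 0.25 × 5.09% = 8.77%.

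**Sensitivity.** With the same d in both arms the ratio is 1.00. The assumed risk hardly matters: with uniform exits and risk ending at exit, 5% and 20% risks both give a ratio of 0.95. Events per person-year return 7.02 per 100 in both arms, so under these assumptions the whole gap comes from time at risk.

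**Limit of a rate per patient-year.** Suppose instead that the whole 10% risk falls in the first 3 months, and all leavers exit at Month 4. The hazard over those months is −ln(0.90)/3 = 0.0351, so mean time at risk in months 0–3 is 0.10/0.0351 = 2.85 months. A completer then contributes 2.85 + 0.90 × 15 = 16.35 person-months and a leaver 2.85 + 0.90 × 1 = 3.75. Person-months per patient are 0.85 × 16.35 + 0.15 × 3.75 = 14.46 at 15% dropout and 0.75 × 16.35 + 0.25 × 3.75 = 13.20 at 25%. Both arms have a crude 10%, yet the rate ratio is 14.46/13.20 = 1.10. At 15% v 30% dropout the false ratio is 1.15, or 1.07 with uniform exits. Rates alone would therefore replace one distortion with another for early events.

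**The case against.** The strongest reply is that the harm is conditional. The plan gives one dropout figure and no reason to expect it to differ by arm, and at equal dropout nothing is biased. This stands and limits the point.

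Second, part of the problem is already visible. Withdrawals and their reasons are tabulated (SAP 5.3), events leading to study termination are a named variable (SAP 4.2.1), safety is descriptive (SAP 5), and the display list in SAP 9 is open-ended. Loss through poor tolerability will thus show up as such. None of this gives time at risk by arm, and an open-ended list permits an exposure table without committing to one. The passage on variable exposure in Protocol 9.6.2 concerns first, last, minimum and maximum assessment values, not event incidence. The Kaplan-Meier and Cox text in SAP 5.2.2 sits under the efficacy variables.

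Third, the follow-up of early leavers works against the bias when completers roll over at Month 18. It does, and the lower two rows of the table allow for it. The direction does not change.

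A reader might also infer that the Phase 2 falls and confusion foretell heavier dropout on azeliragon here. Protocol 1.1.3 reports them at 20 mg/day and says that they were not noted at 5 mg/day, the dose in this trial. They are no ground for predicting unequal dropout.

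Nor does the LOCF justification in SAP 5.2.1 ("assuming no more dropouts in the group treated with azeliragon plus SoC than in the group treated with placebo plus SoC") assume equal dropout or concern adverse events. It is a one-sided condition for an efficacy sensitivity analysis.

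**Conclusion.** The omission is real and the consequence is conditional. Adverse events are summarised without any measure of time at risk, and if dropout differs by arm the arm losing more patients is flattered. At 15% v 25% dropout the understatement is 3% to 9% in relative terms, or about 1 to 3 patients per 400 for an event with a 10% risk. This rests on equal constant hazards, exits unrelated to the event, and assumed dropout by arm. For events clustered soon after first dose the crude percentage is barely affected.

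Two stronger readings are not supported. One is that the planned comparison is biased as it stands: that needs unequal dropout, which the documents neither state nor imply. The other is a larger effect, such as ratios of 0.92 and 0.87 at 15% v 30% dropout with risk ending at exit. That pair averages 22.5%, above the planned ceiling, and leaves out the 3-month follow-up. The point is a worthwhile reporting addition and does not make the safety analysis invalid.

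**What to change.** - **SAP 9:** add a table by arm of treatment duration and patient-years at risk.
- **SAP 5.4.1:** keep the crude percentages. For any TEAE, SAEs, adverse withdrawals and events of special interest, add as descriptive supplements the cumulative incidence of first event by arm (Kaplan-Meier, or Aalen-Johansen where death competes), which needs no constant hazard. Show the incidence per 100 patient-years beside it.
- **At-risk window:** state one end, for example the earliest of the existing 45-day on-treatment limit, last contact and first open-label dose. Apply it to the supplements and to a matching crude count, so that the numerators agree. Otherwise the supplements would drop late follow-up events that the open-ended crude percentage includes.

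The cost is SAP wording and a few more descriptive tables, since dosing, withdrawal and onset dates are already collected. SAP 6.2 does not impute missing days, so a rule for incomplete onset dates is also needed. Rates per patient-year can mislead for early events, which is why the cumulative incidence goes with them. Neither supplement removes bias if patients leave because they are at higher risk of later events. The window and method should be fixed before unblinding.

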#### **5.4.2 Vital Signs**

Subjects with vital signs meeting the criteria in [Section 10](#) of this SAP for values of potential clinical concern will be flagged and summarized. Proportions of subjects with vital signs of potential clinical concern will be examined for the treatment groups.

No formal inferential statistics will be applied to the vital signs data.

For each post-Baseline assessment, descriptive statistics are provided for the assessment value and the change from Baseline to the assessment with mean, median, standard deviation, minimum, and maximum at each assessment time.

#### **5.4.3 Routine Clinical Laboratory Measurements**

Because “exacerbations” of pre-existing abnormalities in laboratory analytes are examined using clinical judgment and are reported as TEAEs, additional analysis on TEAEs is limited to subjects with values that are normal prior to dosing and abnormal after dosing. Potentially clinically significant abnormalities in laboratory analytes are to be reported as TEAEs and summarized as clinical TEAEs.

Subjects with clinical laboratory data meeting the criteria in [Section 10](#) of this SAP for values of potential clinical concern will be flagged and summarized. Proportions of subjects with clinical laboratory values of potential clinical concern will be examined for the treatment groups.

For each post-Baseline assessment, descriptive statistics are provided for the assessment value and the change from Baseline to the assessment with mean, median, standard deviation, minimum, and maximum at each assessment time.

#### **5.4.4 Liver Enzyme Function Tests**

Liver function tests have additional analysis views for this study in accordance with current regulatory guidance. To explore the potential for drug-induced liver injury consistent with *Guidance for Industry “Drug-induced liver injury: premarketing clinical evaluation”* ([CDER, CBER, July 2009](#)), subjects will be summarized and listed who meet the following criteria:

- (1) Elevations in either AST or ALT of at least 3-times the upper limit of normal, and
- (2) An accompanying abnormal bilirubin of at least 2-times the upper limit of normal.

#### **5.4.5 Electrocardiography**

The heart rate, QT, PR, and QRS intervals will be recorded at each assessment time. No formal inferential statistics will be applied to the ECG data.

For each post-Baseline assessment, descriptive statistics are provided for the assessment value and the change from Baseline to the assessment with mean, median, standard deviation, minimum, and maximum at each assessment time.

In addition, the number of subjects with corrected and uncorrected QT values >500 msec will be summarized. Values from individual tracings within the triplicate measurement on Day 1, time 0 hour that are >500 msec will not be included in the categorical analysis unless the average from that triplicate measurement is also >500 msec.

Electrocardiography data will be summarized by Baseline and Change from Baseline to each scheduled assessment time with descriptive statistics.

Corrections to QT intervals will be made by Fridericia's method (QTcF). Categorical analysis will be done consistent with ICH E14, "Clinical evaluation of QT/QTc interval prolongation and proarrhythmic potential for non-antiarrhythmic drugs" (October 2005).

In accordance with ICH E14, subjects will be categorized and summarized as described above according to:

- Absolute QTc interval prolongation:
  - QTc interval > 450
  - QTc interval > 480
  - QTc interval > 500
- Change from Baseline in QTc interval:
  - QTc interval increases from Baseline > 30
  - QTc interval increases from Baseline > 60.

#### **5.4.6 Methodology for Brain MRI (Safety) Analysis**

The primary intent of the MRI assessments was to support eligibility for the trial and key secondary objectives of evaluating the effect of TTP488 on MRI brain volumetric measures. In those subjects with MRI assessments safety evaluation was performed by a central neuroradiologist to evaluate presence and severity of ARIA-E (vasogenic edema), presence and extent of ARIA-H (microhemorrhages), presence of white matter disease, documentation of any other MRI abnormalities.

ARIA-H will be evaluate based on whether microhemorrhages are present, number present, status compared to prior MRI, number of new microhemorrhages since previous MRI, number of microhemorrhages on previous MRI that have resolved, number of microhemorrhages that have increased in size and number that have decreased in size.

#### **5.5 Pharmacokinetics Analysis**

Data resulting from blood sampling for trough concentrations of TTP488 and metabolites (TTP2123, TTP1494, TTP2266) will be collected and analyzed for changes over the 18-month treatment period.

No formal inferential statistics will be applied to the pharmacokinetic data.

## **5.6 Pharmacodynamics Analysis**

Plasma A $\beta$  (total, 1-40 and 1-42) will be analyzed for changes over the 18-month treatment period.

## **5.7 Exploratory Analysis**

The analyses described in this analysis plan are intended to be done. It is noted that additional analyses may be done for this study. These additional analyses may or may not be reported.

## **5.8 Concomitant Medications**

Concomitant medications will be summarized by drug category and listed.

## 6 Data Conventions

The following analysis conventions will be used in the statistical analysis.

### 6.1 Definition of Baseline

For safety evaluations, the Baseline assessment for all measurements will be the latest available, valid measurement taken prior to the initiation study medication, except for electrocardiography (ECG) values: The Baseline assessment for ECG include a triplicate assessment with the baseline value intended to be the arithmetic mean of the values taken at the Baseline assessment that are taken in triplicate.

